7.4. Randomisation, blinding and code-breaking

Within the context of this study it is almost impossible to blind the intervention/control to either the participants or clinicians carrying out the intervention/control because of the type of equipment used.

There are two receiving sites within the study. One will be randomised to being either the intervention site for the first six months followed by six months as the control site. The other receiving site will therefore be randomised as the opposing site acting as the control site for the first six months followed by the intervention site for six months.

The two sites will be randomised as either:

- (1) Intervention (6 months) followed by control (6 months) or
- (2) Control (6 months) followed by Intervention (6 months).

To assist in this randomisation the online tool "Research Randomizer" will be used.

https://www.randomizer.org/

7.5. Protection against bias

7.5.1. Study design

One of the major potential sources of bias in randomised trials is inclusion of different patients in the arms of the trial. This can arise where a large proportion of potentially eligible patients are not included in the trial, and the probability of inclusion is related to the intervention. In this study we aim to identify and include close to 100% of the eligible patients, using a combination of methods for identifying eligible patients, including direct notifications by ambulance clinicians and review of routine ambulance service data.

7.5.2. Threshold for intervention

As ambulance clinicians delivering the interventions will not be blinded, there is a possibility that bias could be introduced by different thresholds between the intervention group (no rigid collar) and control group (standard care including rigid collar). If they believe strongly that non-collar use is effective, some of them may attempt spinal motion restriction without using the collar for patients who are not appropriate, excluded from the study or in the control group of the study and therefore inappropriate. This would result in a group of patients being inappropriately recruited or excluded from the trial potentially masking any beneficial or negative effect of non-collar use. We will use several strategies to prevent this bias from occurring, to detect it if it happens, and to correct it if necessary.

First, the criteria that are used to determine whether spinal motion restriction is appropriate, and hence whether the patient is eligible, are as objective as possible. The guidance in appendix A used by all participating ambulance clinicians in the study to determine when spinal motion restriction is appropriate/not appropriate will continue in the trial. Ambulance clinicians will already be familiar with the application of these criteria, and no change of practice will be needed during the trial with the exception of including those participants over the age of 65 years who have had a mechanism of injury potentially causing injury and complaining of any pain or discomfort in the neck area.

Second, all ambulance clinicians in the study will be trained in the study procedures, to ensure that they understand the rationale for the study and the importance of following the study procedures correctly. The training will include a review of existing evidence so that participating ambulance clinicians understand the current position of equipoise regarding the effectiveness of rigid collars, and discussion of potential sources of bias in the study and the importance of applying the inclusion/exclusion criteria rigorously to both arms. Training will continue throughout the recruitment period, to ensure that any new staff are trained before recruiting, and that important messages are continually reinforced.

Third, we will institute a programme of regular monitoring by analysing the characteristics of patients recruited to the intervention group (non-collar) and control group (standard care including rigid collar) and the proportion of potential spinal cord injured patients recruited, to detect any imbalances that may be caused by different thresholds for spinal motion restriction. If a lower threshold for attempting spinal motion restriction in the intervention group (non-collar use) exists we will find a greater number of recruits and a greater proportion of incidents with spinal motion restriction attempts. The frequency and mechanism of monitoring will be discussed with the Data Monitoring Committee.

If we suspect that a different threshold for spinal motion restriction is being applied by any personnel recruiting to the study, the first step will be to identify the personnel involved and ensure that their training in the trial procedures is up to date, and reinforce the essential messages about the rationale for the trial. The investigators will develop close working relationships with the ambulance clinicians recruiting patients, and will be ideally placed to undertake this role.

Finally, we can, if necessary, correct for any inclusion bias in the statistical analysis of the study, by adjustment of the analysis to take account of imbalance in factors such as mechanism of injury and time since 999 call. We expect any potential inclusion bias to affect only the group of patients least likely to have any detrimental outcomes, and it would not affect patients for whom spinal motion restriction would always be undertaken and therefore a comparison between intervention group (non-collar) and control group (standard care including rigid collar) in the subgroups of patients in whom spinal motion restriction is known to be appropriate would be unaffected.

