The widely accepted methods of cervical spine immobilisation described above have been adopted worldwide and have been relatively unchallenged until the publication of the controversial paper by Hauswald et al. (1998). The Hauswald paper compared two separate emergency departments with similar resources and skill levels that received patients with similar mechanisms of injury. The first department in Malaysia received blunt force trauma patients who had no pre-hospital immobilisation prior to hospital arrival. The second department in New Mexico received blunt force trauma patients who were all immobilised in the traditional manner in the pre-hospital phase of care. Reviewing the remarkable similarities in injury patterns and in hospital management the paper concluded that those patients who received full 'traditional' pre-hospital immobilisation were at higher risk of disability compared to those who did not receive any immobilisation at all. These findings were in stark contrast to the assumptions we have come to accept that traditional immobilisation reduces the risks of disability.

The 2001 Cochrane review into pre-hospital spinal immobilisation identified that, although the judicious and routine use of immobilisation techniques continues, no prospective, randomised control trial (RCT) related to patient outcomes has ever been undertaken (Kwan et al., 2001).

Abram and Bulstrode (2010) critically reviewed the evidence of routinely immobilising trauma patients and its advantages and disadvantages. They concluded that routine immobilisation could be contributing to mortality and morbidity in some patients.

The 2014 guidelines from the National Association of EMS Physicians (NAEMSP) and the American College of Surgeons Committee on Trauma (ACS-COT) highlight that unstable spinal injuries are extremely rare and, as a consequence, a high volume of patients are unnecessarily immobilised with no potential benefit (White et al., 2014).

As the literature has provided little empirical evidence into the benefits of traditional and the potential negative consequences, Myer and Perina (2016) suggest we have created a 50 year culture of immobilising patients for the sake of routine. This culture has perpetuated a fear of the consequences of not routinely immobilising for secondary spinal injury prevention with no real evidence to support this fear.

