6.3. Exclusion Criteria

Exclusion Criteria

The participant may **NOT** enter the study if ANY of the following apply:

- Children aged <18 years,
- Those patients NOT transported to NSECH or JCUH,
- Participant requires airway support for whatever reason,
- The participant has a GCS ≤13,
- The participant is displaying obvious signs of new neurology such as paralysis,
- The participant has significant facial injuries that may benefit from the support a rigid collar may provide.
- The participant has already been immobilised with a rigid collar by a non-study clinician or third party provider prior to **intervention group** clinician assessment.

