7.2. Screening and Eligibility Assessment

The participants will be screened for eligibility by the attending crew based on the Spinal Motion Restriction Screening Tool in appendix A and inclusion/exclusion criteria applied. These clinicians are employed by North East Ambulance Service who are acting as the Participant Identification Centre (PIC)

for patient participants and will also act as a research site for the clinician experience element of the study.

If the patient is positive for immobilisation using the screening tool (appendix A) and in the catchment area of the nominated receiving research sites which will be Northumbria Specialist Emergency Care Hospital (NSECH) at Cramlington, Northumberland or James Cook University Hospital (JCUH) at Middlesbrough then they will be identified as a potential participant in the SMRFS intervention or control group.

Age (unless aged less than 18 years), sex, previous medical history or pregnancy status will not be used to exclude participants.

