7.5.3. Crew Preferences

A potential source of bias is that ambulance clinicians who are motivated to not use the rigid collar may avoid using it during the control phase of their participation in the study. In order to check for this possibility, we will monitor crews attending incidents that are potentially managed with spinal motion restriction and investigate any suspicious patterns such as non-compliance with the allocated treatment. If found, the staff involved will be given extra training in the study procedures.

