8. INTERVENTIONS

The flow chart for all participants in the Spinal Motion Restriction Feasibility Study is shown in appendix D.

Intervention group: Over a six-month period intervention group patients (suspected cervical spine injury – see appendix A for guidelines) will be transported by NEAS crews to the randomised intervention site. See appendix B for SMRF Study Intervention Group Guideline.

Participants will have their cervical spine motion restriction managed in accordance with the proposed flow chart (see appendix B). For these patients unless the exclusion criteria apply, NO rigid collars will be used. The control group will follow existing clinical guidelines and use a rigid collar (appendix E).

9. SAFETY REPORTING (Adverse Event Management)

Use of hard collars in association with blocks and tapes in the manner described above has been accepted practice to reduce the risk of further damage due to movement of potentially unstable injuries for many years. Although there appears to be mounting expert opinion that the application of hard collars may cause more harm than good we must be vigilant against the potential of causing more harm in these patients. If there should be a case of new neurology developing post transfer during the study period the trial would need to be halted while a full and thorough investigation was undergone into whether the use of or lack of a hard collar caused or contributed to deterioration in neurological function. This study is not aimed at underplaying the risk of SCI or the need for appropriate management.

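### Section 7.5.2 says inclusion bias can reach only the lowest-risk patients, yet crews who know the allocation apply severe-end exclusions, one of them worded for the intervention group only

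*Protocol*

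**What the plan says.** Section 7.5.2 of the protocol discusses the risk that unblinded crews apply different thresholds in the two groups. The case it develops is a crew convinced that omitting the collar works. The signal it describes is correspondingly one of excess: more recruits, and a larger share of incidents with spinal motion restriction, in the intervention group. It then gives two assurances. The first is "We expect any potential inclusion bias to affect only the group of patients least likely to have any detrimental outcomes". The second is that "it would not affect patients for whom spinal motion restriction would always be undertaken", so that a subgroup comparison in such patients is unaffected. Section 7.5.3 considers the same preference: "ambulance clinicians who are motivated to not use the rigid collar may avoid using it during the control phase".

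Other sections fix how patients enter or leave the study:

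- Sections 5 and 7.4: allocation is by receiving hospital, for six months at a time.
- Section 7.2: "The participants will be screened for eligibility by the attending crew". Section 7.5.4 says that crews are not blinded.
- Section 6.3 excludes patients needing airway support, with GCS ≤13, with obvious new neurology, or under this criterion: "The participant has significant facial injuries that may benefit from the support a rigid collar may provide".
- Section 6.3 also excludes a patient under this criterion: "The participant has already been immobilised with a rigid collar by a non-study clinician or third party provider prior to" assessment by an intervention-group clinician. It gives no control-group counterpart.
- Section 8, on the intervention group: "For these patients unless the exclusion criteria apply, NO rigid collars will be used".

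The exclusion checklist in the appendices, printed just before the questionnaire items, repeats the section 6.3 list without the prior-collar criterion. It has a field for the reason for exclusion.

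**The concern.** The two assurances describe one mechanism. A crew that favours no collar lowers its threshold, and marginal, low-risk patients are added to the intervention arm. They are worded, however, as covering any potential inclusion bias.

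A second mechanism acts at the other end of the risk scale. In the intervention phase, a crew uneasy about leaving the collar off finds its stated exception in the exclusion criteria. In the control phase a collar is standard, so the same crew lacks that reason to exclude. If borderline severe patients are excluded more readily in one phase, the no-collar arm loses higher-risk patients and looks safer for a reason unrelated to the collar.

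The patients affected would be those whom section 7.5.2 calls safe from bias, so the subgroup comparison offered as a fallback would not be protected. Analysis by intention to treat (section 10.1) cannot restore patients who were never enrolled. The adjustment factors that section 7.5.2 names as examples, mechanism of injury and time since the emergency call, do not directly measure neurology or facial injury.

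**Working it through.** The protocol gives no figure to reproduce: section 10.3 states that there is no power calculation. The check is therefore first one of logic, then an illustration.

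**Passages side by side**

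1. Is allocation known before eligibility is judged? Yes. It is fixed by hospital and phase (sections 5, 7.4), and the unblinded crew screens (sections 7.2, 7.5.4).
2. Do the exclusions concern low-risk patients? Airway support, GCS ≤13 and new neurology do not. What counts as obvious neurology, and whether a significant facial injury may benefit from a collar, need judgement.
3. Does exclusion have the same consequence in both phases? Not as written. Section 8 makes it the exception to collar omission in the intervention group.
4. Are the criteria the same by arm? Not as written. Prior collaring excludes only in the intervention group in section 6.3, and does not appear in the appendix checklist.
5. What would detect the problem? Section 7.5.2 plans to compare patient characteristics by group and the proportion recruited. Section 13.3 monitors recruited participants and patients attended by non-trial vehicles; as worded, patients whom trial crews exclude are in neither group. Section 13.2 audits routine data for potentially eligible patients not reported; a patient recorded as meeting an exclusion may not count as eligible. No comparison of excluded patients by arm is stated.

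**Illustration of detectability**

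From the protocol: 50 per arm (synopsis). Assumed, with no source in the protocol: high-risk share of eligible patients *h* = 10% to 30%; fraction *x* of these excluded from the no-collar arm only = 25% to 75%; no true collar effect; event risk 30% in high-risk patients and 5% in others; two-sided 5% test.

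- High-risk share left in the no-collar arm: p₂ = h(1−x)/(1−hx).
- Power = Φ[(|h−p₂| − 1.96·se₀)/se₁], with se₀ from the pooled proportion and se₁ from the separate proportions.
- Spurious risk difference = (0.30−0.05)·(p₂−h).
- Loss of intervention recruits = hx.

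Example, h = 0.20 and x = 0.50:

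- p₂ = 0.10/0.90 = 0.111; difference 0.0889; pooled proportion 0.1556.
- se₀ = √(0.1556·0.8444·2/50) = 0.0725; se₁ = √(0.16/50 + 0.0988/50) = 0.0719.
- Power = Φ[(0.0889 − 0.1421)/0.0719] = Φ(−0.74) ≈ 23%.
- Event risk 10.0% in control and 7.8% with no collar: difference −2.2 points.

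| h | x | p₂ | Power | Spurious difference (points) | Recruits lost |
|---|---|---|---|---|---|
| 10% | 25% | 7.7% | 6% | −0.6 | 2.5% |
| 10% | 50% | 5.3% | 14% | −1.2 | 5% |
| 10% | 75% | 2.7% | 32% | −1.8 | 7.5% |
| 20% | 25% | 15.8% | 8% | −1.1 | 5% |
| 20% | 50% | 11.1% | 23% | −2.2 | 10% |
| 20% | 75% | 5.9% | 56% | −3.5 | 15% |
| 30% | 25% | 24.3% | 9% | −1.4 | 7.5% |
| 30% | 50% | 17.6% | 30% | −3.1 | 15% |
| 30% | 75% | 9.7% | 73% | −5.1 | 22.5% |

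If every high-risk patient were excluded (x = 100%), power would be 63% to 99%. The normal approximation is rough at these small counts. Recruitment moves down, opposite to the excess that section 7.5.2 describes.

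**The case against.** The strongest reply is that the protocol already watches for this. Section 7.5.2 commits to looking for any imbalance in characteristics and in the proportion recruited, and the sentence about excess recruits only gives the expected sign under a lower threshold. Section 7.5.1 aims at close to 100% inclusion, sections 13.2 and 13.3 add audits and arm-level monitoring, and the checklist records why a patient was excluded. Clinicians volunteer (section 7.1) and are trained to apply the criteria rigorously to both arms. All of this stands. A reader might infer that high-risk patients could leave the no-collar arm undetected, or that monitoring counts recruits only; the text does not support either reading.

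Three further inferences also go too far:

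- *That crews may exclude anyone they think would benefit from a collar.* The clause covers significant facial injuries only and is listed for both arms, so bias requires differential use. Nothing in the protocol shows that these patients are at the highest neurological risk.
- *That exclusion by collar-favouring crews is the likelier direction.* Section 3 does report that "This culture has perpetuated a fear of the consequences of not routinely immobilising for secondary spinal injury prevention", but this is a cited article's general view, not evidence about these crews.
- *That exclusion is the only way to use a collar in the intervention phase.* The flow charts are not visible in the text. A crew could also deviate from allocation, which section 7.5.3 monitors and which leaves the patient in the assigned arm.

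The size is also modest for the rarest outcome. At the cited confirmed rate of under 0.5% (section 3), 50 patients would give fewer than 50 × 0.005 = 0.25 spinal cord injuries, so any shift would show mainly in commoner outcomes. None of this rescues the two assurances, which are stated without the qualification they need.

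**Conclusion.** The point holds as a defect in what section 7.5.2 claims and in how eligibility is written. The statement that inclusion bias reaches only the lowest-risk patients, and leaves the clearly appropriate subgroup untouched, does not follow from the protocol's own criteria. Differential exclusion at the severe end is possible and would favour the no-collar arm on safety. Whether it will occur cannot be settled from the protocol.

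The prior-collar exclusion needs no assumption about crew behaviour: as worded in section 6.3, eligibility differs by arm, and the appendix checklist disagrees. The protocol does not show which way that difference shifts risk.

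Detection would be weak rather than absent. The power range of 6% to 73%, and the spurious differences of 0.6 to 5.1 points, rest wholly on the assumed shares and risks and are illustrations, not estimates. A feasibility study can tolerate some imbalance. It should not present a subgroup comparison as free of inclusion bias when the design does not secure that. The change should be made, and it is small.

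**What to change.** 1. In section 7.5.2, delete the statements that bias affects only the patients at least risk and that the appropriate subgroup is unaffected. Do not present the subgroup comparison as free of inclusion bias.
2. State there and in section 13.3 that monitoring looks for imbalance in both directions, including fewer or milder recruits in the intervention phase.
3. Tabulate exclusions by criterion, site and phase from the checklist field, compare excluded patients between arms, and report the counts in the CONSORT flow.
4. Reconcile the intervention-only prior-collar exclusion in section 6.3 with the appendix checklist, and state that the criteria are applied identically in both phases. The clinical content of each criterion, including the facial-injury clause, is for the sponsor.

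Cost: a wording amendment, one extra table from a field already on the form, and a less favourable statement about protection against bias.

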7.5.3. Crew Preferences

A potential source of bias is that ambulance clinicians who are motivated to not use the rigid collar may avoid using it during the control phase of their participation in the study. In order to check for this possibility, we will monitor crews attending incidents that are potentially managed with spinal motion restriction and investigate any suspicious patterns such as non-compliance with the allocated treatment. If found, the staff involved will be given extra training in the study procedures.

7.5.4. Blinding

Due to the nature of the interventions, ambulance clinicians cannot be blinded, and will be aware of treatment allocations. Ambulance emergency operation centre dispatch personnel will be blinded to the allocation of the ambulance service vehicles, to ensure that there is no bias in whether a vehicle with a study trained clinician (intervention or control) or non-study vehicle is sent to an incident that is likely to involve spinal motion restriction. Patients themselves will be aware of their treatment allocation at the time of the intervention. Research clinicians assessing outcomes at the receiving hospitals not be blinded to treatment group due to the contents of the patient notes and liaising with the patients during their inhospital phase who were not blinded.

7.6. Study Visit

There are two elements to the study. In the first element there will be two research sites located at Northumbria Specialist Emergency Care Hospital (NSECH) and James Cook University Hospital (JCUH) to follow up Patients who are participants. The second element will involve NEAS as a research site to follow up clinicians as participants to understand their experience of the study.

Patient participants will be approached while in the Emergency Department (ED) after the CT report has been received or up to 72 hours if admitted. Those who are discharged without CT or prior to the research clinician visit will be followed up via telephone interview. The study visit will be a single visit and will not be repeated unless the participant wishes to have time to reflect upon the information and make a delayed consent at a time and date suitable for them.

Participants may opt to be informed of the results of the study via the consent form if they wish to do so.

Base line variables will not be possible to collect prior to entry into the study and can only be completed from a patient perspective.

The study visit will include the following questions during the Participant Experience questionnaire and will be collected in person by the research co-ordinator at NSECH or JCUH unless participant wishes to delay this and complete during a home visit or via email:

_				
1.	\odot	•••		?
How did you feel when the ambulance crew assessed and prepared you for transport?				
Free Text:				
2.	YES	,	NO	?
Did you feel you received sufficient explanation as to why your neck movements were being controlled?				
Free text:				
3.	:	(i -i)		?
How did you feel about the way your neck movements were controlled during your transfer / transport?				
Free Text:				
4a.	YES		NO	?
Did you have any concerns about how your neck was controlled while you were transferred to hospital?				

Free text:			
4b.			
40.	YES	NO	, ,
Mara varia agracina abaut bau varia			•
Were your concerns about how your neck was controlled taken into			
account by the ambulance crew?			
Free text:			
5.			_
3.	YES	NO	Š
			•
Did you experience any breathing			
problems during your management			
and/or transport to hospital?			
Free text:			
6.			_
0.	YES	NO	Š
			•
Did you experience any pain or			
discomfort as a result of the control of			
your neck movements during			
transfer?			
Free text:			
7			
7.	YES	NO	7
		1.10	•
Did you experience any other			
complications as a result of the			
